#### **5.5.1.3. Human Anticipated Therapeutic Dose Determination**

A target blood exposure of 7632 ng.h/mL [approx.  $AUC_{(0-12h)}$ ], corresponding to plasma  $AUC_{0-12h}$  of 12.745  $\mu\text{g.h/mL}$  (i.e. plasma  $AUC_{0-24h}$  of 25.49  $\mu\text{g.h/mL}$  following a 25 mg/kg dose of GSK3186899 to BalbC mice [[GlaxoSmithKline Document Number 2018N377947\\_00](#)]) will be leveraged to select plausible therapeutic doses for humans. These estimates were determined from the data obtained after 10 days treatment of BalbC mouse, after which efficacy has been demonstrated. An estimated dose of 600mg b.i.d./day was predicted to provide a plasma  $AUC_{0-24h}$  of 31.95  $\mu\text{g.h/mL}$  on day 10 ( $>$  mouse target plasma  $AUC_{0-24h}$  of 25.49  $\mu\text{g.h/mL}$ ). Hence, a dose of  $\sim$ 600 mg b.i.d/day was considered as anticipated therapeutic dose (ATD) assuming a dose-independent bioavailability (F). However, if during dose escalation, clinical doses show a dose-dependent F, similar exposure are also expected to occur at a dose of 1200mg BID/day.

#### **5.5.2. Maximum SAD Dose Determination**

A nominal maximum SAD dose of 2500mg is proposed for this study to achieve  $>$ target plasma  $AUC_{0-24h}$  for maximum pharmacology. This is based on the consideration that if a dose-dependent bioavailability decrease is observed as per the simulations presented, then a nominal dose of 1200 mg BID will be anticipated to produce desired therapeutic effect. If 1200 mg BID is ATD, then to support this dose in multiple ascending dose (MAD) study, exposures coverage from nominal SAD dose is desired. Hence, a maximum nominal SAD dose of 2500 mg is considered in this FTIH to support the development of GSK3186899. Accumulation following repeat dosing is not evident from simulations. The exposures from this dose have several-fold margins to the NOAELs from female rat (with dose independent F: 3-fold for Cmax & 7-fold for  $AUC_{0-24h}$ ; with dose dependent F: 7-fold for Cmax & 14-fold for  $AUC_{0-24h}$ ). The nonclinical data support the conduct of clinical studies in healthy volunteers up to 3 weeks duration up to 3-fold below the mean systemic exposure at the female NOAEL of 100 mg/kg/day in the rat 4-week study (AUC: 434  $\mu\text{g.h/mL}$ , Cmax: 46.2  $\mu\text{g/mL}$ ) with appropriate monitoring in place. The dose escalation will proceed up to nominal top dose of 2500 mg in dose independent F scenario to provided PK stopping criteria is not met; considering the PKPD variability and translational uncertainty of the preclinical data to provide flexible dosing regimen option.

### 5.5.3. Dose Escalation Plan

The dose escalation will follow a scheme as shown in [Table 5](#) with target plasma  $AUC_{0-24h}$  determined from the dose-response relationship from the BalbC mouse efficacy model. Based on the exposures from starting dose, appropriate modifications will be made to the subsequent proposed nominal doses. All available data will be evaluated for dose-escalation decisions. Based on emerging clinical data, appropriate changes to the dose-escalation step-size will be made. The decision to dose escalate, or to halt escalation, will be made by the DEC and will be guided by the safety and SAD PK stopping criteria as outlined below ‘Dose escalation/stopping criteria’.

### 5.5.4. Safety Margins

[Table 5](#) below lists the predicted safety cover for GSK3186899 at various anticipated doses in the SAD FTIH study assuming dose independent and dose dependent bioavailability, respectively, and indicate that the anticipated doses have several-fold margins of safety to the NOAEL exposures from female rat:

**Table 5 Projected mean plasma GSK3186899  $AUC_{0-24h}$  and Cmax assuming dose-independent and dose-dependent bioavailability (F) scenarios following single oral doses of GSK3186899, with Fold Cover to preclinical NOAEL exposures alongside showing the nominal SAD doses with the fold dose-escalation**

Dose Level	Dose # (mg)	Fold Escalation	Predicted Human Plasma Exposures*				Safety Margins ( $AUC_{0-24h}$ )		Safety Margins (Cmax)	
			$AUC_{0-24h}$ ( $\mu\text{g.h/mL}$ )		Cmax ( $\mu\text{g/mL}$ )					
			Dose IDP F	Dose DP F	Dose IDP F	Dose DP F	Dose IDP F	Dose DP F	Dose IDP F	Dose DP F
1	30	-	0.82	0.78	0.16	0.15	528	558	283	299
2	60	2	1.61	1.45	0.33	0.29	269	299	142	158
3	120	2	3.23	2.68	0.65	0.54	134	162	71	86
4	300	2.5	8.23	5.76	1.64	1.14	53	75	28	40
5	600	2	16.59	9.96	3.28	1.97	26	44	14	23
6	1200	2	32.77	17.04	6.55	3.41	13	25	7	14
7	2500	2.1	68.72	31.91	13.66	6.34	6	14	3	7

**Key:**

*IDP = independent; DP = dependent; F = bioavailability*

#Actual doses may be altered based on emerging PK data

\*The predicted human exposures are in blood and the animal exposures are in plasma. Human Blood to plasma ratio (B/P ratio = 0.60) is used for conversion of predicted blood exposures (X1.67) to obtain human plasma exposures.

NOAEL exposures in Female rat: AUC = 434  $\mu\text{g.h/mL}$ ;  $C_{\max}$  = 46.2  $\mu\text{g/mL}$ . Safety margin = NOAEL exposure parameter value/predicted human plasma exposure parameter.

### **5.5.5. Multiple Ascending Dose (MAD)**

Three dosing cohorts will be used for MAD. The selection of appropriate daily doses will be performed upon consideration of available safety, tolerability and PK data from SAD part and/or any preceding repeat dose cohorts in MAD and limiting exposure to be no less than 5-fold below the NOAEL of the rat 28-day toxicity study (AUC: 434  $\mu\text{g.h/mL}$ ,  $C_{\max}$ : 46.2  $\mu\text{g/mL}$ ). Twice-daily (BID) dosing is currently planned for MAD, but other dosing options may be considered based upon the safety/tolerability and pharmacokinetics observed in SAD part. For MAD dose selection, three doses based on exposures from SAD that support single/repeated dosing will be chosen identifying maximum anticipated therapeutic dose. Once this dose is identified, three cohorts will be chosen for the MAD doses: cohort 1 (0.5X anticipated therapeutic dose), cohort 2 (0.75X maximum anticipated therapeutic dose) and cohort 3 (maximum anticipated therapeutic dose). It should be noted that calculated steady state plasma  $AUC_{0-24h}$  exposure on day 10 will be used as part of PK stopping criteria following repeat dosing. PK sampling is proposed for 0-12h for BID dosing or 0-7h for TID dosing on day 10 at steady state; hence  $AUC_{0-24h}$  (day 10) will be derived as  $2 \times AUC_{0-12h}$  or extrapolated  $AUC_{0-8h} \times 3$  for BID or TID dosing, respectively.

### **5.6. Dose Escalation**

As part of this decision-making process, the DEC may decide to escalate or de-escalate the dose in Part A and/or B. The dosing schedule may also be adjusted to expand a cohort to further evaluate safety or PK findings at a given dose level, or to add cohorts to evaluate additional dose levels. Dosing may also be halted before all planned dose levels have been completed if the stopping criteria has been met or if review of the data determines that evaluation of further dose levels is not necessary to meet the study objectives.

There will be an open and closed part to the dose escalation meeting. At the beginning of the meeting blinded data will be discussed in an open forum with the Principal Investigator in attendance. If required, the data will then be reviewed in an unblinded fashion by the unblinded members of the DEC. These unblinded members include the clinical pharmacology modeling and simulation department (CPMS) pharmacokineticist and GCSP representative.

### 5.6.1. Dose Escalation Committee

The decision to proceed to the next dose level of GSK3186899 in each Cohort will be made by a DEC consisting of the Principal Investigator (or appropriate designee), Medical Monitor, GSK Clinical Investigational lead and/or Study Team Leader, GSK pharmacokineticist, a GSK GCSP representative and GSK Statistician. All GSK personnel will remain blinded throughout the course of the study, with the exception of the CPMS pharmacokineticist and GCSP representative. Additional internal GSK safety representatives may be consulted and included in the dose escalation decision making, as deemed necessary by the DEC.

Details of the DEC membership, data to be reviewed and stopping criteria will be outlined in the DEC charter.

### 5.6.2. Part A

**Dose escalation meeting:** The decision to proceed to the next dose level of GSK3186899 will be made at a DEC meeting based on:

- all available safety and tolerability data from a minimum of 48 hours post-dose from a minimum of 4 or more participants who have received GSK3186899 at the current dose level. Individual safety data (AEs, laboratory safety tests, telemetry, ECGs and vital signs) will be reviewed.
- all available safety and tolerability data accumulated from preceding dose levels and available PK data from current (minimum of 4 or more participants) and preceding dose levels.

**Safety review meeting:** The decision to proceed from Cohort 1 Period 4 (DL4) to Cohort 2 Period 1 (DL4), and Cohort 3 Period 1 (DLX) to Cohort 3 Period 2 (DLX-FD) will be made by the Principal Investigator and Medical Monitor based on:

- all available safety and tolerability data from a minimum of 48 hours post-dose from a minimum of 4 or more participants who have received GSK3186899 at the current dose level. Individual safety data (AEs, laboratory safety tests, telemetry, ECGs and vital signs) will be reviewed.

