### **8.1.1. Dose Adjustment/Stopping Pharmacokinetic Criteria**

The following dose adjustment / PK stopping criteria will apply:

- A maximum  $C_{max}$  of 15.4 $\mu$ g/mL or 9.24 $\mu$ g/mL and a total daily AUC of 145  $\mu$ g.h/mL or 86.8  $\mu$ g.h/mL for SAD or MAD part, respectively, will not be intentionally exceeded and will be used as safety threshold exposures for PK stopping criteria as per GSK renal safety panel recommendations. These exposures are 3-fold or 5-fold below the NOAEL exposures of 46.2  $\mu$ g/mL for  $C_{max}$  and 434  $\mu$ g.h/mL for total daily AUC in the 28-day female rat study for SAD or MAD part, respectively.
- Dose escalation will be stopped if any single participant reaches exposures greater than PK stopping criteria threshold exposures. We intend to use the PK dose escalation rule for progression to the next dose or dose adjustment which will involve establishing a relationship between dose vs. exposures ( $AUC_{0-24h}$  &  $C_{max}$ ) using a power model and linear mixed effect modeling once PK data are available from a minimum of two prior dose levels. This model will be continually updated with incorporation of new dose levels as they become available. This developed model will be used to project mean  $AUC_{0-24h}$  and  $C_{max}$  for the next dose level.
- If mean group exposure from the maximum total daily dose is predicted to reach the PK stopping criteria exposures, dose escalation will be stopped, or dose adjustment will be planned, as appropriate. For any dose adjustments for the next dose, an increase or decrease in the nominal dose will occur if the projected exposure for the

next dose deviates by more than 30% of the initial projected mean systemic exposure. The GSK study team will decide based on emerging safety, tolerability and PK information whether to evaluate any lower doses or repeat doses already evaluated in remaining periods to collect additional safety and PK data.

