#### **8.1.7. Individual Safety Stopping / Withdrawal Criteria**

- If a participant experiences a serious or severe clinically significant AE that in the clinical judgement of the Investigator, after consultation with the medical monitor, is possibly, probably or definitely related to investigational product.
- The participant becomes pregnant.
- The participant initiates treatment with any prohibited medications.
- If any of the liver chemistry, QTc, renal and/or adrenal stopping criteria are met (See Section 8.1.3 -Section 8.1.6).
- The participant develops stomach erosion as confirmed clinically and following a gastro enterology specialist's opinion for further management, and endoscopy (if required).

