### **8.1.9. Study Treatment Restart or Rechallenge**

If any stopping criteria are met by any participant in this study, study treatment restart or rechallenge is not allowed.

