3. PLANNED ANALYSES

3.1. Interim Analyses

No formal interim analyses (IA) are planned for this study. However, regular dose escalation meetings, an informal IA and safety review meetings are planned to be performed at different time points described below.

- Dose escalation meetings are planned to review the safety, tolerability, and PK data prior to:
 - each dose escalation in Part A (single dose) – Cohorts 1 and 2,
 - initiation of the food effect Cohort 3, and
 - each dose escalation in Part B (repeat dose) – prior to initiation of Cohorts 5 and 6.
- An informal IA to review the safety, tolerability, and PK data from Part A is planned prior to:
 - progression to Part B.
- Additional instream safety review meetings including all safety and tolerability data only are planned prior to:
 - progression to Cohort 2 in Part A
 - progression to Period 2 in the food effect Cohort 3.

There will not be a formal database freeze performed for this informal IA. Data included for these analyses will be as complete and clean as possible based on continuous data review and monitoring activities.

The final study analysis post- database freeze will include all data captured in the study database.

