3.1.1.3. Safety review meetings

The decision to proceed from Cohort 1 Period 4 to Cohort 2 Period 1 and similarly progress from Cohort 3 Period 1 (DLX) to Cohort 3 Period 2 (DLX-FD) will be made by the Principal Investigator and Medical Monitor based on all available safety and tolerability data from a minimum of 48 hours post-dose from a minimum of 4 or more participants who have received GSK3186899 at the current dose level. Individual safety data (AEs, laboratory safety tests, telemetry, ECGs and vital signs) will also be reviewed. PK data will not be included in these reviews.

The study team will remain blinded until the database freeze, except for the unblinded site Pharmacist, unblinded study Pharmacokineticist and SMG Pharma Safety representative.

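### The review before Cohort 3 Period 2 leaves out Period 1 PK, so a participant over a single-dose exposure limit could be redosed at DLX without a required check

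*Protocol*

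**What the plan says.** Protocol 5.6.2 describes two kinds of decision in Part A. The DEC decision to raise the dose needs PK from at least 4 participants at the current level. The decision to proceed from "Cohort 3 Period 1 (DLX) to Cohort 3 Period 2 (DLX-FD) will be made by the Principal Investigator and Medical Monitor based on" safety and tolerability data: adverse events, laboratory tests, telemetry, ECGs and vital signs. PK is not listed.

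The SAP makes the omission explicit. Section 3.1 says "Additional instream safety review meetings including all safety and tolerability data only are planned prior to" two steps, one of them Cohort 3 Period 2. Section 3.1.1.3 says "PK data will not be included in these reviews". Protocol 10.6 does promise a PK review ahead of the food-effect investigation, but SAP 3.1 places it before Cohort 3 starts, so it cannot cover Cohort 3 Period 1.

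On exposure limits, Protocol 8.1.1 sets single-dose values of 15.4 ug/mL for Cmax and 145 ug.h/mL for total daily AUC, which "will not be intentionally exceeded and will be used as safety threshold exposures for PK stopping criteria". For one participant over a limit it states this consequence: "Dose escalation will be stopped if any single participant reaches exposures greater than PK stopping criteria threshold exposures". Section 8.1.7 lists individual withdrawal criteria and includes "If any of the liver chemistry, QTc, renal and/or adrenal stopping criteria are met", with a cross-reference to 8.1.3 to 8.1.6; it does not list 8.1.1. Section 8.1.9 says "If any stopping criteria are met by any participant in this study, study treatment restart or rechallenge is not allowed".

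**The concern.** The protocol sets an exposure limit that a single participant can breach. Cohort 3 is where everyone on active drug is given the same dose level a second time, yet the review that releases the second dose is not asked to look at exposure after the first. The stated single-participant consequence, stopping escalation, does not clearly apply, because DLX to DLX-FD is the same dose.

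Cohort 3 has up to 14 participants, all on active drug and without sentinels. Cohorts 1 and 2 supply about 6 active participants per dose level (12 at DL4 if it is repeated as planned), too few to rule out an exceedance among 14 new people. At stake is whether a limit that the protocol calls a safety threshold can be acted on at this step.

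**Working it through.** **Limits.** The plan's figures reproduce from the female rat NOAEL exposures: 46.2/3 = 15.4 ug/mL, and 434/3 = 144.7, rounded to 145 ug.h/mL.

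**Inputs.**
- Protocol 5.4 puts DLX around the therapeutically relevant dose. The target plasma AUC(0-12h) is 12.745 ug.h/mL per dose (5.5.1.3).
- Table 5, 600 mg, dose-independent bioavailability: AUC 16.59 ug.h/mL, Cmax 3.28 ug/mL. Scaling gives target Cmax = 3.28 x 12.745/16.59 = 2.52 ug/mL, or 16% of the limit.
- Within-subject CV for Cmax is 30% (10.2): log SD = sqrt(ln 1.09) = 0.294.
- Between-participant spread is an assumption. I use log SD 0.30 and, as a wider case, CV 50% (the Table 3 clearance value, itself assumed): sqrt(ln 1.25) = 0.472. Total log SD is sqrt(0.30² + 0.294²) = 0.420 or sqrt(0.472² + 0.294²) = 0.556.
- Table 5 is headed as projected means. I show each value read as an arithmetic mean and as a median.

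**Chance that at least 1 of 14 exceeds 15.4 ug/mL.** With lognormal Cmax and total log SD s, z = ln(15.4/C)/s if C is the median, and z = [ln(15.4/C) + s²/2]/s if C is the mean. Then p = P(Z > z), and the cohort chance is 1 − (1 − p)^14.

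Example, twice the target, s = 0.420: as a median, z = ln(15.4/5.04)/0.420 = 2.66, p = 0.0039, cohort chance 5.3%. As a mean, z = 2.87, p = 0.0020, cohort chance 2.8%.

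| Cmax (multiple of target) | s = 0.420: mean / median | s = 0.556: mean / median |
|---|---|---|
| 2.52 (1) | 0.004% / 0.011% | 0.3% / 0.8% |
| 3.28 (1.3; 600 mg in Table 5) | 0.07% / 0.16% | 1.5% / 3.7% |
| 3.78 (1.5) | 0.3% / 0.6% | 3.5% / 7.8% |
| 5.04 (2) | 2.8% / 5.3% | 14% / 27% |

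The AUC limit binds less. With s = sqrt(ln 1.25 + ln 1.04) = 0.512 and values read as medians, the cohort chance is 0.001% at 12.745 ug.h/mL and 0.5% at 25.49.

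**Chance that someone exceeds the limit, is redosed, and exceeds it again.** This uses a bivariate normal for log Cmax in the two periods, with correlation 0.30²/0.420² = 0.511 or 0.472²/0.556² = 0.721, and assumed fed:fasted ratios of 0.8 to 1.0. At twice the target, values read as medians, this happens in 0.15% to 0.5% of 14-person cohorts with s = 0.420 and in 5% to 10% with s = 0.556.

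**Reading the rules together.** Section 8.1.1 sits under 8.1, on discontinuing study treatment, and its title calls its contents stopping criteria. The closing sentence of 8.1.2 also treats the PK criteria as one set of stopping criteria among several. Section 8.1.9 covers any stopping criteria. So 8.1.9 probably bars redosing a participant over a limit. The bar depends on knowing the Period 1 exposure, which the review before Period 2 leaves out.

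**The case against.** The strongest reply is that this is a coherent design. PK is required where the dose rises and left out where it does not (DL4 to DL4, DLX to DLX-FD). On this view the promise not to exceed the limits intentionally governs the choice of dose, and it is met by having the DEC pick an already evaluated DLX with modelling of fed exposure. Food is expected to leave exposure the same or slightly lower (5.4). Much of this stands, and it is why the likelihood is low. It does not supply a check on the individual about to be redosed.

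Three stronger readings are tempting, and the documents do not support them.

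- A reader might infer that nobody can see an exceedance. SAP 3.1.1.2 has PK data passed to the study pharmacokineticist for review during the study, Cohort 3 is open label (7.3.2), and both decision-makers sit on the DEC with a pharmacokineticist (5.6.1). Section 8.1.1 also lets the study team decide on emerging PK "whether to evaluate any lower doses or repeat doses already evaluated in remaining periods to collect additional safety and PK data", and 5.6 lets the DEC de-escalate or halt. These are permissions; none requires Period 1 PK before Period 2. The DEC charter, which may say more, is not among the documents.
- A reader might infer that the protocol allows redosing above a limit. Sections 8.1 to 8.1.2 with 8.1.9 point the other way. The fault is that 8.1.7 omits PK and the review lacks the data.
- A reader might take the SAP 2.3 note, that DL7 was dropped for higher than expected exposures, as a sign that exceedance is likely. It shows the exposure control working, and the DEC would know those exposures when choosing DLX. To reach a cohort chance of 16% to 26% (mean or median, s = 0.420) one must assume 800 mg at 1.5 times prediction. By interpolation in Table 5, Cmax is then 4.37 x 1.5 = 6.55 ug/mL and AUC is 21.98 x 1.5 = 32.97 ug.h/mL, or 2.6 times the target, against the intent of 5.4.

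**Conclusion.** The point holds as a gap in a required check. At this one redosing step the plan does not require anyone to compare a participant's Period 1 exposure with the limits in 8.1.1, and the SAP rules PK out of the review. The rule that probably bars redosing therefore cannot be applied there.

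The likelihood is low: under 1% of 14-person cohorts would have anyone over the Cmax limit at the target exposure, and about 3% to 27% at twice the target. These figures rest on lognormal exposure, assumed between-participant variability and proportional scaling from Table 5; DLX and its exposures are not in the documents. The clinical weight is also small: the limit is one third of a 28-day rat NOAEL exposure, the two single doses are at least 10 days apart, and the review does see laboratory results. It is worth changing because the change is cheap.

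**What to change.** For the Cohort 3 Period 2 review only:

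- Remove the PK exclusion in SAP 3.1 and 3.1.1.3.
- Add to Protocol 5.6.2 each participant's available Period 1 Cmax and AUC(0-24h), read against 15.4 ug/mL and 145 ug.h/mL.
- State in 8.1.7 or 8.1.9 that a participant over either limit is not redosed at DLX and that the case goes to the DEC.
- Add this event to SAP Table 3 (8.2.4), which covers only consent withdrawal, incomplete dosing and adverse-event drop-out. Keep the participant's Period 1 value in the food-effect mixed model and treat Period 2 as missing at random, since the missingness depends on the observed Period 1 value.

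Dropping the whole participant would bias the ratio upward. With fasted first, a true ratio of 1, values read as medians and s = 0.420, the complete-pairs factor is exp[(1 − 0.511) x 0.420 x φ(z)/Φ(z)]. This is 1.002 at twice the target and 1.011 at Cmax 6.55. I give no residual figure for the SAP 8.2.5.1 model. It includes period and unstructured covariance, and if every participant is fasted first, as 5.6.2 writes it, food and period cannot be separated; Protocol 7.3.1 instead randomizes to fed or fasted.

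Cost: wording only, with no new samples and no blind at risk. Period 1 assays for up to 14 participants must be ready within the washout of at least 10 days. That looks feasible, since current-level PK is already required between periods in Cohorts 1 and 2 under the same washout, although assay turnaround is not documented. Each participant withheld costs one fed/fasted pair from the drop-out allowance (14 recruited for 12 evaluable, minimum 10). Two such losses would use all of it.
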